AZD9291 is an oral, potent, selective, irreversible inhibitor of both EGFR-TKI sensitising and T790 mutations in NSCLC with a significant selectivity margin over wild-type EGFR. AZD9291 will be administered orally as a tablet once a day. A cycle of treatment is defined as 21 days of once daily AZD9291 treatment.

On clinic days on which PK samples are scheduled to be taken, the dosing should be delayed until arrival at the clinic and until the pre-dose ECG has been performed followed by the pre-dose PK sample. Patients should not take their dose until instructed to do so by site personnel.

Duration of treatment

Patients in both cohorts (40 mg and 80 mg once daily) may continue on treatment with AZD9291 until a treatment discontinuation criterion is met. There is no maximum duration of treatment as patients may continue to receive AZD9291 beyond RECIST 1.1 defined progression as long as they are continuing to receive clinical benefit, as judged by the investigator (see Section 5.2).

Outcomes variable(s)

Primary endpoints/variables

PK exposure parameters derived from plasma concentrations of AZD9291, and metabolites AZ5104 and AZ7550.

Following the single dose part (or first dose) of the study:

Maximum plasma concentration (C_{max}), time to Cmax (t_{max}), terminal rate constant (λz), terminal half life ($t_{\nu_{2}\lambda z}$), area under the plasma concentration-time curve from zero to 24 hours (AUC₍₀₋₂₄₎), from zero to 72 hours (AUC₍₀₋₇₂₎), from zero to the time of the last measurable concentration (AUC_(0-t)) and from zero to infinity (AUC), apparent plasma clearance (CL/F) (AZD9291 only), apparent volume of distribution (AZD9291 only), mean residence time (MRT), where possible.

Following the multiple dose part of the study:

Cycle 2 Day 1

Maximum plasma concentration at steady state ($C_{ss max}$), time to $C_{ss max}$ ($t_{ss max}$), minimum plasma concentration at steady state ($C_{ss min}$), area under the plasma concentration-time curve from zero to the end of the dosing interval (AUCss), apparent plasma clearance at steady state (CL_{ss}/F) (AZD9291 only), extent of accumulation on multiple dosing (R_{AC}), time dependency of the pharmacokinetics where possible.

Cycle 1 Day 8

C_{C1D8 max}, t_{C1D8 max}, C_{C1D8 min}, AUC_{tau}

Trough concentrations on Cycle 1 Day 8, day 15 and Cycle 2 day 1.

The ratio of metabolite to AZD9291 will also be calculated.

Secondary endpoints/variables

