3.1 Overall study design and flow chart

This is a phase I, open-label, two parts (Part A and Part B) study to determine the pharmacokinetics of AZD9291 administered orally at two dose levels (40 mg and 80 mg) in patients with locally advanced or metastatic NSCLC who have progressed following prior therapy with an approved EGFR TKI agent (+/- additional chemotherapy regimens).

Approximately 24 patients will enter into this study, with 12 patients at each dose level

- Cohort 1 will investigate the pharmacokinetics of single then multiple dosing of AZD9291 at 40 mg once daily dose.
- Cohort 2 will investigate the pharmacokinetics of single then multiple dosing of AZD9291 at 80 mg once daily dose.

The enrollment of Cohort 2 will start after Cohort 1 finishes the enrollment. The first 12 patients enrolled in the study will be in 40 mg dose Cohort.

Patients will be administered a single dose of AZD9291 on Day 1, Cycle 0 at the beginning of Part A period. From Day 2 to Day 6, no treatment will be given, but PK samples will be obtained; on Day 8 (Cycle1, Day1), the patients will be administered AZD9291 once daily on a continuous schedule, ie, no break in AZD9291 dosing. Part A will complete after Cycle 4 treatment and Part B will start without treatment interruption.

Patients in both cohorts should continue on treatment with AZD9291 until a treatment discontinuation criterion is met. There is no maximum duration of treatment as patients may continue to receive AZD9291 beyond RECIST 1.1 defined progression as long as they are continuing to receive clinical benefit, as judged by the investigator.

The whole study will be divided nominally into two parts: Part A will assess the pharmacokinetics and preliminary efficacy and safety of AZD9291 at 40 mg and 80 mg respectively, and Part B will assess only the safety and efficacy data of AZD9291.

Following completion of the Part A, patients will automatically continue to Part B.

There are two data cut offs:

- 1. PK and preliminary efficacy and safety data base lock will take place approximately 3 months after LSI and after the part A completes, to allow all patients have two tumor assessments after the first dose.

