- 2. Safety and efficacy data base cut off will take place at the earlier time point when either all patients have discontinued treatment and completed 28 days post treatment safety follow-up, or 12 months after the last patient enrolled started investigational product. Data analysis will be performed and a Clinical Study Report (CSR) written based on this data set. Any patients still receiving investigational product at the time of this data cut-off will be able to continue to receive AZD9291 while deriving clinical benefit. Such patients will continue to be monitored for all Serious Adverse Events up to 28 days after the last dose of investigational product. Drug Accountability information must still be collected until all patients have completed treatment.

A CSR will be issued after PK and preliminary efficacy and safety data base lock; a CSR addendum will be issued for updated safety and efficacy information after final safety and efficacy data base lock.

Figure 1 Study flow chart

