7.2 Determination of sample size

The primary objective of this study is to characterise the pharmacokinetics (PK) of AZD9291 after a single then multiple oral doses of AZD929. The key secondary objective is to investigate the safety and tolerability of AZD9291 to recommend dose(s) for evaluation in future clinical studies. Hence the number of patients in the cohorts has been based on the desire to obtain adequate tolerability, safety and pharmacokinetic data while exposing as few patients as possible to the investigational product and procedures. Tumour response as measured using RECIST 1.1 will be assessed to provide preliminary anti-tumour activity in targeted patient population.

Approximately 12 patients with advanced NSCLC will be enrolled in each cohort

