7.7 Methods of statistical analysis

The statistical analyses will be performed by or other designated third party providers, under the direction of the Biostatistics Group, AstraZeneca.

Demographic data

Characteristics of the patients, including medical history and disease characteristics at baseline will be listed for each patient and summarised by dose group.

Reasons for discontinuation of investigational product will be listed including the study day of treatment discontinuation and will be summarised by dose group.

Exposure

Exposure to investigational product ie, total amount of study drug received will be listed for all patients.

Total exposure and total time on study (date of last dose minus date of first dose) will be summarised by the following: mean, standard deviation, minimum, maximum, median and number of observations. In addition, the number and percentage of patients with at least one dose interruption/dose delay and at least one dose reduction will be presented separately for the initial period defined as 21 days of multiple dosing (cycle 1) and for any time following this initial period of the study.

Safety

Safety data will not be formally analysed. All patients who receive at least one dose of AZD9291 will be included in the assessment of the safety profile (safety analysis set). At the end of the study, appropriate summaries of all safety data will be produced, as defined below.

Data from all cycles of initial treatment will be combined in the presentation of safety data. AEs will be listed individually by patient and dose group. For patients who have a dose modification, all AEs (due to drug or otherwise) will be assigned to the initial dose group. The number of patients experiencing each AE will be summarised by the Medical Dictionary for Regulatory Activities (MedDRA) system organ class, MedDRA preferred term and CTCAE grade. The number and percentage of patients with adverse events in different categories (eg, causally related, CTCAE grade \geq 3 etc) will be summarised by dose group, and events in each category will be further summarised by MedDRA system organ class and preferred term, by dose group. SAEs will be summarised separately if a sufficient number occur.

Any AE occurring before the first dose of investigational product (ie, before study Day 1) will be included in the data listings but will not be included in the summary tables of adverse events.

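### At the first data lock, crude all-cycle AE percentages by dose can overstate 40 mg relative to 80 mg, because the 40 mg cohort enrols first and has longer potential follow-up

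*Protocol*

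**What the plan says.** **Enrolment.** Protocol section 3.1: "The enrollment of Cohort 2 will start after Cohort 1 finishes the enrollment". The first 12 patients go to 40 mg. Section 7.2: "Approximately 12 patients with advanced NSCLC will be enrolled in each cohort".

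**First cut-off.** Section 3.1: "PK and preliminary efficacy and safety data base lock will take place approximately 3 months after LSI and after the part A completes". The clinical study report (CSR) follows this lock; updated safety and efficacy go into an addendum.

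**Second cut-off.** Section 3.1 takes the earlier of two events: "either all patients have discontinued treatment and completed 28 days post treatment safety follow-up", "or 12 months after the last patient enrolled started investigational product".

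**AE presentation.** Section 7.7: "Data from all cycles of initial treatment will be combined in the presentation of safety data". Numbers and percentages of patients with AEs are given by dose group. AEs up to 28 days after discontinuation enter the summaries. Safety is descriptive, with no formal analysis. Total exposure and time on study are summarised, but this item does not say by dose group. Dose interruptions and reductions are split into Cycle 1 and later; AEs are not.

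**Use.** Section 7.2 makes safety and tolerability the key secondary objective, with the aim of recommending dose(s) for later studies.

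**The concern.** The last patient enrolled is an 80 mg patient. A lock timed from that patient gives every 40 mg patient longer potential follow-up than every 80 mg patient. A crude percentage of patients with an AE rises with time observed, so equal risk per month at the two doses would still show more AEs at 40 mg.

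The direction matters. The artefact raises the lower dose's figure and so can hide a real excess at the higher dose. No test is planned, so the side-by-side percentages are what a reader of the CSR will use to judge tolerability by dose.

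**Working it through.** **1. The plan's own timing.** The synopsis defines a cycle: "A cycle of treatment is defined as 21 days of once daily AZD9291 treatment". Part A is Cycle 0 (7 days) plus Cycles 1 to 4: 7 + 4 × 21 = 91 days = 2.99 months. The second tumour assessment, 6-weekly from Cycle 1 Day 1, falls at 7 + 2 × 42 = 91 days. The stated interval of about 3 months from last subject in to the first lock is therefore reproduced.

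**2. Accrual span A (not stated; derived).** The synopsis has the last subject completing Part A in Q1 2016. Less 91 days, the last subject enters between 2 October and 31 December 2015. With a first subject in Q3 2015, A is about 0 to 6 months. Section 5.6 starts the study in Q2 2015, which would allow up to about 9 months; the two start dates should be reconciled. The range used is A = 2 to 6 months.

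**3. Potential follow-up.** Take 24 evenly spaced starts over A, the first 12 at 40 mg. Neighbouring starts are A/23 apart, so the cohort means differ by 12A/23: 1.04 months at A = 2 and 3.13 months at A = 6.

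**4. Crude AE risk with equal hazards.** Assumptions not in the protocol:
- constant AE hazard h = −ln(1 − p)/3, the same at both doses, with 3-month risk p = 10%, 20% or 40%;
- exponential time on treatment, rate d = ln 2/median, median 6, 9 or 12 months.

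From section 7.7, each patient's AE window is the shorter of time on treatment plus τ = 28 days (0.92 months) and time to cut-off C. Then

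P(no AE) = e^(−hτ) · d/(d+h) · [1 − e^(−(d+h)(C−τ))] + e^(−d(C−τ) − hC).

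Example at the first lock: A = 4, median 9, p = 20%, so h = 0.0744 and d = 0.0770.
- 40 mg, mean C = 6.04: 0.934 × 0.509 × 0.539 + 0.430 = 0.686, risk 31.4%.
- 80 mg, mean C = 3.96: 0.934 × 0.509 × 0.369 + 0.589 = 0.765, risk 23.5%.

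Averaging over the 12 individual starts per cohort gives 31.3% vs 23.4%, a gap of 7.9 points with no true difference.

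**5. Whole grid (gap = 40 mg minus 80 mg, percentage points).**

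| A (months) | Mean potential follow-up, first lock | Gap, first lock | Mean potential follow-up, 12-month branch | Gap, 12-month branch |
|---|---|---|---|---|
| 2 | 4.5 vs 3.5 | 2.2 to 7.6 | 13.5 vs 12.5 | 0.5 to 1.5 |
| 3 | 5.3 vs 3.7 | 3.1 to 10.2 | 14.3 vs 12.7 | 0.6 to 2.1 |
| 4 | 6.0 vs 4.0 | 3.9 to 12.2 | 15.0 vs 13.0 | 0.7 to 2.6 |
| 6 | 7.6 vs 4.4 | 5.0 to 14.9 | 16.6 vs 13.4 | 0.9 to 3.4 |

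The smallest second cut-off value is 0.48; subtracting the rounded percentages (64.0 − 63.6) gives 0.4. One patient in 12 is 8.3 points.

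**6. The other branch of the second cut-off.** If all patients have stopped and completed 28 days, nobody is cut short by the calendar and enrolment order produces no gap. Under the same model this branch has probability below 0.5% at a median of 6 months or more on treatment, but 25% (A = 3) to 35% (A = 6) at a median of 3 months.

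**7. With a common window.** Every patient can reach 91 days by the first lock. Cutting both cohorts at 91 days makes C equal, and the gap is 0.

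**The case against.** **It is SAP detail.** Common-window tables and exposure-adjusted rates are often left to the SAP, which is not shown and may contain them. Section 7.7 forbids neither. That stands, and it keeps the point minor. But the protocol does commit to a specific display, and that display has this property.

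**Longer at every cut-off.** A reader might infer that 40 mg is always followed longer. The documents do not support this, because the second cut-off has the all-stopped branch. Only potential follow-up is longer, too: a 40 mg patient who stops early has a shorter AE window than an 80 mg patient still on drug.

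**Larger figures.** Treating everyone as on treatment until the cut-off, 1 − e^(−ht) with h = 0.05, 0.10 or 0.20 per month gives 26% vs 18%, 45% vs 33% and 70% vs 55% at 6 vs 4 months (8 to 15 points), and 2 to 5 points at 15 vs 13 months. This ignores discontinuation. At the same 4-month accrual, the grid above gives about 4 to 12 points and then at most 2.6.

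**The first lock is preliminary and the data are imprecise.** The protocol calls safety at that lock preliminary, and section 7.7 places the safety summaries at the end of the study. With 12 per group, the 95% half-width for a difference in proportions is 1.96 × √(2p(1−p)/12), or 32 points at p = 20% and 40 at 50%. Section 3.2 also says 80 mg had already been selected for later trials. All this limits the consequence. It does not remove a bias of known direction from the report issued at that lock.

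**Reinforcement by the attribution rule.** AEs stay with the initial dose group after a dose change, so a reader might see AEs after a 40 to 80 mg increase adding to the same bias. That increase requires at least 6 months on 40 mg and progression (section 5.2), so it can scarcely operate at the first lock. The same rule charges AEs after an 80 to 40 mg reduction to 80 mg, the opposite direction. It is not counted here.

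**Conclusion.** The point holds for the first lock. Sequential enrolment, a lock timed from the last patient and crude all-cycle percentages together give a false excess at 40 mg of about 2 to 15 points under equal hazards, from well under one patient in 12 to nearly two. At the second cut-off it is about 0.5 to 3.4 points, less than one patient, and enrolment order contributes nothing on the all-stopped branch.

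These sizes rest on assumed accrual of 2 to 6 months, a median of 6 to 12 months on treatment and a constant hazard. If AEs start mainly in the first 91 days, the gap shrinks; if there is a pause between cohorts, it grows. Severity is minor: descriptive safety only, with no planned test affected.

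A reader might go further and conclude that the all-cycles table should lose its place as the main display. The documents do not support that: dosing is open-ended, and only that table shows late events.

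**What to change.** Keep the all-cycles AE table. At least for the first lock, add to section 7.7 or the SAP:

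- AE percentages by dose group over a common window, from first dose to the end of Cycle 4 (91 days), or to discontinuation plus 28 days if earlier; and/or exposure-adjusted rates by dose group (patients with an event per unit of time at risk);
- time on study and total exposure summarised by dose group.

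The rates remove the artefact only if the hazard is roughly constant; the common window does not need that assumption.

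Cost: one extra set of tables. AE start dates and dosing dates are already collected, so no new data or design change is needed. The common-window table does not show late toxicity, which is why it sits beside the all-cycles table and does not replace it.

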5.2 Dose and treatment regimens

AstraZeneca will supply AZD9291 as tablets for oral administration as a single daily dose of 40 mg and 80 mg respectively. At each dispensing visit, sufficient AZD9291 for 21 days treatment, plus overage, will be dispensed.

Patients will be administered a single dose of AZD9291 on Day 1, Cycle 0 at the beginning of Part A period. From Day 2 to Day 6, no treatment will be given, but PK samples will be obtained; on Day 8 (Cycle1, Day1), the patients will be administered AZD9291 on a continuous schedule. Part A treatment will complete at the end of Cycle 4 and treatment in Part B will continue.

Patients may continue receiving AZD9291 until treatment discontinuation criteria are met. Patients may receive AZD 9291 beyond disease progression as long as they are considered to receive clinical benefit continuously judged by the treating physician.

Patients who were started and have remained on treatment at a dose of 40mg for at least 6 months, have shown clinical benefit (as judged by the investigator) and have then developed RECIST confirmed disease progression, and did not experience any treatment – related grade 3 AE when treated at dose of 40mg, may have dose increased to 80mg after agreement in advance between the Investigator and AZ Study Physician. 80mg has been declared to have an acceptable tolerability profile by the Safety Review Committee.

Tablets should be taken whole with water, 240ml being the recommended volume for PK days. AZD9291 can be taken with or without food at the same time each day. Patients will be required to fast (water only) for at least 8 hours prior to the collection of a fasting glucose sample as per the study plan (Table 2).

Doses should be taken approximately 24 hours apart at the same time each day. Doses should not be missed. If a patient misses taking a scheduled dose, within a window of 12 hours, it is acceptable to take the dose. If it is more than 12 hours after the dose time, the missed dose should not be taken, and patients should be instructed to take the next dose at the next scheduled time. If a patient vomits after taking their AZD9291, they should not make up for this dose, but should take the next scheduled dose.

Any change from dosing schedule, dose interruptions, dose reductions should be recorded in the eCRF.

Assessment timings if dosing is interrupted

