5.2.1 Toxicity management

If a patient experiences a CTCAE grade 3 or higher and/or unacceptable toxicity (any grade) not attributable to the disease or disease-related processes under investigation, where the Investigator considers the AE of concern to be specifically associated with AZD9291, dosing will be interrupted and supportive therapy administered as required in accordance with local practice/guidelines.

In cohort 1, if the toxicity resolves or reverts to \leq CTCAE grade 2 within 3 weeks of onset, treatment with AZD9291 may be restarted at the same dose. In cohort 2, if the toxicity resolves or reverts to \leq CTCAE grade 2 within 3 weeks of onset, treatment with AZD9291 may be restarted at the same dose (80 mg) or a lower dose (40 mg) using the rules below for dose modifications (Table 1) and with discussion and agreement with the AstraZeneca Study Team Physician as needed. There will be no individual modifications to dosing schedule in response to toxicity, only potential dose reduction or dose interruption.

If the toxicity does not resolve to \leq CTCAE grade 2 after 3 weeks, then the patient should be withdrawn from the study and observed until resolution of the toxicity.

Starting Dose	Reduced AZD9291 Dose
80 mg daily	40 mg daily
40 mg daily	no dose reduction

Table 1Dose interventions

On resolution of toxicity within 3 weeks:

• If an AE subsequently requires dose interruption, AZD9291 may restart at the same dose or the reduced dose (as per Table 1), on resolution/improvement of the AE at the discretion of the Investigator.

If new or worsening pulmonary symptoms (eg, dyspnoea) or radiological abnormality suggestive of interstitial lung disease is observed, an interruption in study treatment dosing is recommended, and the AstraZeneca study physician should be informed. A questionnaire regarding the results of the full diagnostic workup (including high-resolution computed tomography (HRCT), blood and sputum culture, haematological parameters) will be sent to Investigators. It is strongly recommended to perform a full diagnostic workup, to exclude

alternative causes such as lymphangitic carcinomatosis, infection, allergy, cardiogenic edema, or pulmonary hemorrhage. In the presence of confirmatory HRCT scans where other causes of respiratory symptoms have been excluded, a diagnosis of interstitial lung disease should be considered and study treatment permanently discontinued.

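### Read literally, the safety rule in Protocol section 7.7 counts adverse events that first arise on 80 mg after a permitted 40 to 80 mg increase in the 40 mg column

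*Protocol*

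**What the plan says.** **Dose increase.** Under Protocol section 5.2, a patient who started on 40 mg and "remained on treatment at a dose of 40mg for at least 6 months", showed benefit, then had RECIST progression, and had no treatment-related grade 3 AE on 40 mg, "may have dose increased to 80mg after agreement in advance between the Investigator and AZ Study Physician".

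**Dose reduction.** Section 5.2.1 and Table 1 allow an 80 mg patient to resume at 40 mg after toxicity. A 40 mg patient has no lower dose.

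**Attribution of AEs.** Section 7.7 (Safety) says: "Data from all cycles of initial treatment will be combined in the presentation of safety data". It then lists AEs by patient and dose group and continues: "For patients who have a dose modification, all AEs (due to drug or otherwise) will be assigned to the initial dose group". Counts and percentages of patients in categories such as causally related or grade 3 and above "will be summarised by dose group, and events in each category will be further summarised".

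**Status and use.** Section 7.7 also says "Safety data will not be formally analysed". Section 7.2 gives the key secondary objective as "to investigate the safety and tolerability of AZD9291 to recommend dose(s) for evaluation in future clinical studies".

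**The concern.** Keeping a patient's events under the starting dose makes sense when the dose is lowered for toxicity, because the reduction is itself a consequence of the starting dose. An increase is different. The patient is then exposed to a higher dose, and a new event on that dose says little about how 40 mg is tolerated. The sentence in section 7.7 makes no such distinction.

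With about 12 patients per cohort and no model behind the tables, the displayed percentages are the evidence on tolerability by dose. A few events in the wrong column would be visible in the rates, and the reader would get no warning from the exposure tables: section 7.7 counts interruptions, delays and reductions there, but not increases.

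**Working it through.** **1. The plan's own figure.** There is none to reproduce. The protocol states no AE rate, no expected number of escalations and no power calculation; only the cohort size of about 12 (section 7.2) is usable. All risks below are assumptions.

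**2. Tracing one event.** A Cohort 1 patient is increased under section 5.2 and has a first AE on 80 mg. Could any rule keep it out of the 40 mg column?
- Section 7.6 attributes by actual dose, but only for erroneously treated patients. A permitted increase is not an error.
- The reference in section 7.7 to cycles of initial treatment might be meant to stop at escalation, but the term is not defined and the attribution sentence covers all AEs. If it did stop there, AEs on 80 mg after escalation would appear in no summary that section 7.7 describes.
- Nothing else in the protocol cuts AE counts at the dose change or tabulates by dose at onset.

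**3. Weight of one patient.** 1/12 = 8.3 percentage points.

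**4. Expected size.** Let e be the number escalated out of 12, q40 the risk of a given AE while on 40 mg, q80 the risk in the 80 mg cohort, and r the risk of a first onset after escalation.

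Rate shown for 40 mg = q40 + (e/12) × (1 − q40) × r

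Assume q40 = 10%, q80 = 30% and r = 30%. For e = 1: 0.10 + (1/12) × 0.90 × 0.30 = 0.1225.

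| e | 40 mg column | Difference shown (true: 20 points) |
|---|---|---|
| 0 | 10.0% | 20.0 |
| 1 | 12.25% | 17.75 |
| 2 | 14.5% | 15.5 |
| 4 | 19.0% | 11.0 |
| 6 | 23.5% | 6.5 |

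Setting r equal to the full 80 mg risk is generous: escalated patients have already tolerated 40 mg and will usually have less time on 80 mg. A second set lets r vary. Assume q40 = 20%, q80 = 40% and r from 10% to 40%. The chance that at least one patient enters the 40 mg column for that AE only because of onset on 80 mg is 1 − (1 − 0.8r)^e.

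| e | Difference shown (true: 20 points) | Chance of at least one such patient |
|---|---|---|
| 1 | 19.3 to 17.3 | 8% to 32% |
| 3 | 18.0 to 12.0 | 22% to 69% |
| 6 | 16.0 to 4.0 | 39% to 90% |

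**5. Treatment-related grade 3 events.** Escalation requires that none occurred on 40 mg, so every escalated patient enters the 80 mg period with a count of zero. A first such event on 80 mg adds a full 8.3 points to the 40 mg column for an event that, by the eligibility condition, did not happen on 40 mg.

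**6. Timing.** Cohort 1 enrols first (section 3.1). If the 12-month trigger sets the final cut-off, each Cohort 1 patient has at least 12 months of potential follow-up, which leaves 12 − 6 = 6 months or more after the earliest possible escalation. The first lock is about 3 months after the last patient is enrolled, when only early Cohort 1 patients could have reached 6 months.

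**The case against.** **The rule may have been written for reductions only.** Section 5.2.1 uses the term dose modification for toxicity-driven reductions, while section 5.2 calls escalation an increase. That reading is coherent, but it is not stated, and the text as it stands covers any modification. Under either reading a clarifying sentence is needed.

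**The number escalated may be very small.** Escalation needs six months on 40 mg, benefit, progression, no related grade 3 event and prior agreement. Nothing in the protocol supports four or six out of 12. This stands: zero and one are as admissible as the larger values. With 12 per group, the standard error of a 10% versus 30% difference is √(0.10 × 0.90/12 + 0.30 × 0.70/12) = 0.158, about 16 points, so a shift of a few points lies well inside chance variation.

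**A reader might infer that the rule always makes 80 mg look no worse than 40 mg.** The protocol does not support that. The same sentence leaves AEs that start on 40 mg after a reduction in the 80 mg column, where they can only raise the 80 mg rate. The one-sided effect holds for escalated patients, not for the rule as a whole.

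**The consequences are limited.** Safety is descriptive, the cohorts are sequential, and sections 3.2 and 5.3 say that 80 mg was already selected for later trials. AEs are also listed by patient, so a careful reader could find them. This stands too, but section 7.2 still names a dose recommendation as the purpose, and a listing does not correct a summary table.

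**Conclusion.** The point holds as a defect in a stated rule. Read literally, sections 5.2 and 7.7 together place AEs with first onset on 80 mg in the 40 mg column. For escalated patients the error runs one way, at 8.3 points per added patient, and it can attribute to 40 mg a related grade 3 event that the escalation condition excludes there.

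The size cannot be fixed from the protocol. It is nil with no escalation and about 2 points (12.25% against 10%) for one escalated patient under the assumed 10% and 30% risks. It grows beyond that only if several patients escalate. The effect is on displayed rates, not on a test, and mainly on the final cut-off and the CSR addendum. It does not show that the overall 40 versus 80 mg comparison is biased in a known direction.

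**What to change.** In section 7.7:
- Limit attribution to the initial dose group to dose reductions and interruptions.
- For escalated Cohort 1 patients, count AEs and exposure under 40 mg only up to the first 80 mg dose.
- Show AEs with onset from that dose onwards in a separate column for patients escalated from 40 mg to 80 mg.
- Report the number escalated, and show dose at onset in the AE listing.
- Show exposure time beside the rates.

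The cost is a sentence or two and one table column. AE start dates (section 6.4.3) and changes to dosing (section 5.2) are already collected.

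Three downsides should be stated:
- Late effects of 40 mg that surface just after escalation move to the new column.
- Worsening of an AE already present at escalation cannot be split by onset date, because section 6.4.3 keeps only the maximum grade, except for skin reactions and diarrhoea.
- Follow-up under 40 mg then ends at an escalation triggered by progression, while 80 mg patients may continue beyond progression. Follow-up is therefore unequal, which is why exposure time belongs beside the rates.

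The change concerns tabulation only and leaves the clinical escalation rule as it is.
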